5.1 Description

Choline, which is considered part of the Vitamin B-complex, is an essential nutrient normally consumed on a daily basis in many foods. Supplemental choline will be administered in the form of a fruit-flavored drink mix containing choline bitartrate (compounded for the study by Fagron, St. Paul, MN under IND#107085). Balchem (New Hampton, NY) manufactures the choline bitartrate to USP standards. The parent will add the powder to plain water. The matching placebo drink mix (without choline bitartrate) will also be provided by Fagron. Material will be stored, labeled, allocated, and dispensed by the University of Minnesota's Investigational Drug Service (IDS) Pharmacy.

5.2 Treatment Regimen

Choline will be administered at a dose of 19 mg per kg once daily, as an oral solution for nine months. Placebo will be administered as an oral solution once daily for nine months. Choline will be administered under FDA Investigational New Drug Application #107085. Parents will be informed that choline is being regulated as an investigational drug for purposes of this clinical trial.

CONFIDENTIAL

This material is the property of the University of Minnesota. Do not disclose or use except as authorized in writing by the study sponsor

5.3 Method for Assigning Subjects to Treatment Groups

Randomization will be managed by using a computer procedure for randomization and tracking. A block randomization with variable block sizes will be used to maximize unpredictability of assignment. The University of Minnesota Investigational Drug Service will have the randomization code and will assign subjects and distribute the test article according to the randomization schedule.

5.4 Preparation and Administration of Study Drug

Fagron will prepare the choline fortified fruit-flavored drink mix and placebo drink mix for the study (IND#107085). Participating families will be provided with a supply of the material in the form of individual packages. The parent / guardian will prepare the drink by adding the powdered drink mix to plain water and will then administer it to the child. The parent/guardian will be trained to prepare and administer the test article at the time of the baseline visit.

5.5 Subject Compliance Monitoring

The parent/guardian of each subject will be asked to keep all empty study packets in a provided Ziploc bag. Self-addressed, postage-paid large envelopes will be provided to participant families to facilitate the return of empty packets. At the time of Visit 8 and Visit 11, the parent/guardian will be asked to bring all used and unused packets of the test article. Study staff will count the used and unused packets. Information will be recorded on the compliance case report form for each follow-up visit.

Significant non-compliance will be reported to the investigator after each follow-up visit. Compliance will be discussed and encouraged at each follow-up visit including telephone visits.

5.6 Prior and Concomitant Therapy

At baseline, and at every follow-up visit, the parent/guardian will be asked to provide information about any over-the-counter or prescription medications the subject is currently taking or has been given since the last visit. The parent/guardian will be asked to provide the name of the substance, the dose, the starting date and the stopping date.

After enrollment, the new initiation of nutritional supplements containing choline or betaine will be disallowed. All other concomitant therapies, including potential behavioral interventions, will be allowed and recorded.

5.7 Packaging

The test article, a powdered drink mix, will be packaged in individual foil packets. The powdered drink mix in each foil pack will contain either choline bitartrate or placebo. The test article will be delivered by courier from the manufacturer (Fagron) to the

CONFIDENTIAL

This material is the property of the University of Minnesota. Do not disclose or use except as authorized in writing by the study sponsor

University of Minnesota Investigational Drug Service where the labels will be prepared and where the material will be kept prior to distribution to research participants. Each foil packet will be labeled with a study number, date of manufacture, a code by which the contents (choline bitartrate vs. placebo) can be tracked, cautionary note, and indication of "investigational drug" status.

5.8 *Blinding of Study Drug*

Each packet of test article will be coded with an arbitrary code number. The University of Minnesota Investigational Drug Service will keep the link between these codes and the contents (choline bitartrate vs. placebo). The investigators will remain blinded throughout the study. The study statistician, [name], will have access to the link and, therefore, will be unblinded.

5.9 *Receiving, Storage, Dispensing and Return*

5.9.1 *Receipt of Drug Supplies*

Balchem, the manufacturer of the active agent and the placebo, will ship the product to a compounding pharmacy (Fagron). The transportation and packaging will take place according to GMP (good manufacturing practices). Fagron will then ship the material in sealed foil packets to the University of Minnesota Investigational Drug Service (IDS). IDS will perform an inventory, complete a drug receipt log, and return any damaged material to the manufacturer. This will be documented and the study sponsor will be notified. There are no special storage requirements for this product.

5.9.2 *Dispensing of Study Drug*

The Investigational Drug Service will assign the test article (choline bitartrate or placebo) to each participant by consulting the randomization schedule. The investigators will pick up the coded test article from the IDS in several amounts. Initially, 30 packets will be distributed to participating family at the study baseline visit. The remaining material will be distributed in batches of 60 packets.

The investigator will keep a log onsite to ensure all medication that is dispensed is recorded the day of the baseline visit and the days of shipment.

5.9.3 *Return or Destruction of Study Drug*

At the completion of the study, there will be a final reconciliation of test article distributed, consumed, and remaining. This reconciliation will be logged on the drug reconciliation form, signed and dated. Any discrepancies noted will be investigated, resolved, and documented prior to destruction of unused study drug. Drug destroyed on site will be documented in the study files.

CONFIDENTIAL

This material is the property of the University of Minnesota. Do not disclose or use except as authorized in writing by the study sponsor

6. Study Procedures

6.1 Visits 1, 8, & 11 (Baseline and follow-up assessment visits)

Participants and their parent/guardians identified as described in Section 4.3 of this protocol will be asked to come for a baseline visit (Visit 1). This visit is expected to last for approximately 3 to 3.5 hours. Visits 8 and 11 will be similar, but slightly shorter (2.5 to 3 hours) because several tasks are not repeated. The following procedures will occur:

- Consenting process (Visit 1 only);
- Medical history (Visit 1 only) and physical exam
- Concomitant medications will be recorded
- Height
- Weight
- Head circumference
- Facial photograph to allow for detailed measurements (Visit 1 only)
- Blood pressure
- Blood collection for choline and metabolite (betaine, phosphatidylcholine, sphingomyelin, and trimethylamine-N-oxide (TMAO) level (3 ml tube).
- Plasma extracted from this whole blood will be analyzed for measures of immune function (cytokines) and micro-RNA..
- Extraction of DNA sample from any blood sample for single nucleotide polymorphisms related to endogenous choline synthesis (PEMT rs12325817)
- Astley & Clarren's FASD diagnostic evaluation including a photograph of the child's face for computer measurement and analysis (Visit 1 or Visit3)
- Stanford Binet Intelligence Scales, Fifth Edition (Visit 1 and 11 only)
- Elicited Imitation Paradigm, including video-recording to facilitate scoring afterward
- Minnesota EF Scale (MEFS), Early Childhood Version
- NIH Toolbox Flanker Inhibitory Control and Attention Task
- Beery Developmental Test of Visual-Motor Integration (VMI) (any visit)
- Scales of Independent Behavior (SIB) (any visit)
- Child behavioral questionnaires (CBCL); a parent-report instrument
- 24-hour Diet interview (for the parent/guardian to complete about the subject)
- Child Eating Behavior Questionnaire (CEBQ); a parent-report instrument
- Randomization (Visit 1 only)
- Training on how to store, mix, and administer the study medication (Visit 1 only)
- Adverse events will be recorded (Visits 8 & 11 only)
- Dispense a supply of the test article (30 packages at Visit 1)
- Provide instructions for returning for the next follow-up visit (Visits 1 & 8 only)

6.2 Visits 2, 3, 4, 5, 6, 7, 9, 10 & 12 (compliance/safety phonecontacts)

At each of these visits, study staff will place a phone call to the participant's parent/guardian. The following information will be collected:

CONFIDENTIAL

This material is the property of the University of Minnesota. Do not disclose or use except as authorized in writing by the study sponsor

- Adverse events will be recorded
- Concomitant medications will be recorded (Visits 2,3,4,5,6,7,9 & 10)
- Any challenges with compliance related to administration of the study medication or completing the medication diary (Visits 2,3,4,5,6,7,9 & 10)

Visit 2 will occur 14 days after the baseline visit; Visit 3 will occur at Month 1 after baseline; Visit 4 will occur at Month 2 after baseline; Visit 5 will occur at Month 3 after baseline; Visit 6 will be at Month 4 after baseline; Visit 7 will be at Month 5 after baseline; Visit 9 will be at Month 7 after baseline; Visit 10 will be at Month 8; Visit 12 will be at Month 10 after baseline (one month after discontinuation of the test article). The acceptable visit window for each of these visits is +/- 7 days for Visit 2 and +/-14 days for the remainder of the visits. Each phone call is expected to last approximately 15 minutes. The purpose of Visit 12 is to collect potential adverse event data after the participant is no longer on the test agent.

6.3 Return assessment visit (1R21AA019580 / 4R33AA019580) (2B)

- Consenting – using separate consent form; Assenting if age =>7 years
- Height
- Weight
- Elicited Imitation Paradigm, including video-recording to facilitate scoring afterward
- The NIH Toolbox Picture Sequence Memory Test
- The NIH Dimensional Card Sort Test
- The NIH Picture Sequence Memory Test
- The Narrative Memory subtest from the NEPSY-II
- Stanford Binet Intelligence Scales, Fifth Edition
- Child behavioral questionnaires (CBCL)
- 24-hour Diet interview

6.4 Second Return Visit (1R21AA019580 / 4R33AA019580) (2C)

- Consenting – using separate consent form; Assenting for those age =>7 years
- Delis-Kaplan Executive Function System (DKEFS) Trail Making and Color-Word Interference subtests
- NIH Toolbox List Sorting task
- Wechsler Intelligence Scale for Children – working memory subtests
- Child Behavior Checklist (CBCL)
- 1 hour MRI scan
- Subjects will be scanned at the Center for Magnetic Resonance Research on a Siemens Prisma scanner. High resolution structural scans will be collected
- MRI scans will not be interpreted clinically. Group MRI analysis will be done using already published approaches.
- Use of radiation: NA – MRI does not use ionizing radiation
- Use of Center for Magnetic Resonance Research: This study uses the University of Minnesota's CMRR and follows all CMRR protocols and procedures.

CONFIDENTIAL

This material is the property of the University of Minnesota. Do not disclose or use except as authorized in writing by the study sponsor

- De-identified neuroimaging data will be stored locally on servers supported by the Center for Magnetic Resonance (CMRR).
- De-identified cognitive and behavioral data will be stored in a secure, HIPAA-compliant RedCap database supported by the University of Minnesota.
- Data elements to be stored will include processed, de-identified neuroimaging results, de-identified neurocognitive test results, and de-identified behavioral questionnaire data.

NOTE: If a participant has recently participated in one of our other protocols, and there is recent appropriate MRI or neuropsychological data, signed permission will be obtained to utilize those data for the purposes of this protocol (in addition to the standard consent and assent forms for this study).

NOTE: Missing data for cognitive measures in studies of children with neurodevelopmental disorders are common (because of attention deficits, non-compliance, etc.). Behavioral checklists are always presented with the option to skip items if they are uncomfortable. Therefore, missing cognitive test data and behavioral checklist data are within protocol and not considered deviations.

7. Statistical Plan

7.1 Sample Size Determination

For purposes of sample size determination, the dependent measure was the percent of correct items on delayed recall of the EI task (averaged across two events per timepoint). The effect size from our completed trial was $d=0.66$. A power analysis was carried out using Optimal Design Software for Multi-level and Longitudinal Research (Version 3.01) to determine the sample size that would be necessary to detect a difference in linear change between treatment and placebo groups with this effect size (Feingold 2009). The analysis assumed that the data would be analyzed using a mixed models repeated measures design for a person-randomized trial, with an effect size $d=.66$, and a two-tailed type I error of 0.05. To achieve 80% power, a sample size of 58.5 participants (approximately 30 per treatment arm) is necessary. This is consistent with the significant group difference that was observed in the pilot trial. The sample size for the proposed study will therefore be fixed at 60 children. Combining participant data

CONFIDENTIAL

This material is the property of the University of Minnesota. Do not disclose or use except as authorized in writing by the study sponsor

for some outcome measures from the first set of pilot studies (N=60) and the proposed study (N=60) will provide additional power to further evaluate age, sex, and PEMT genotype as moderating variables.

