Our research group has recently completed the first pilot studies to evaluate choline supplementation as a neurodevelopmental intervention in children with FASD. We first conducted a double-blind, randomized, placebo-controlled pilot study (R21AA019580) that focused on establishing the safety and tolerability of choline in children with FASD (n=20) (Wozniak, Fuglestad et al. 2013). That study evaluated the safety of choline (there were no serious adverse events) and demonstrated high tolerability (children received partial or full doses on 87% of 270 days in the study). We recently completed a larger double-blind, randomized, placebo controlled trial that included a total of 40 additional participants, ages 2.5 to 5 years (R33AA019580). Compared to placebo, choline supplementation improved 2-3 year old children's performance on an elicited imitation paradigm, a hippocampus-dependent memory task. These data are outlined in the preliminary studies section below. The results comprise the first available human evidence that the pre-clinical findings in rodents may translate to humans. The results from our initial two studies of choline in children with FASD directly inform the next phase of this work which will include 1. Testing a modified dosing scheme based on the efficacy and side effect data collected in the previous trials; 2. Determining the longevity of the cognitive changes attributable to choline; 3. Examining the specificity/generalizability of choline's effects by measuring additional cognitive domains; 4. Further evaluating a choline-specific gene as a potential

CONFIDENTIAL

This material is the property of the University of Minnesota. Do not disclose or use except as authorized in writing by the study sponsor

moderator of treatment response. The genomic hypothesis centers around a single nucleotide polymorphism (SMP) that is involved in endogenous choline synthesis (phosphatidylethanolamine N-methyltransferase (PEMT) rs12325817 SNP). The SNP is associated with significantly greater susceptibility to dietary choline insufficiency (Fischer, da Costa et al. 2010). The hypothesis is that children with one or two alleles of rs12325817 (CG or CC genotype) will show a significantly larger response to choline treatment on measures of cognitive functioning compared to those with the normal genotype (GG) because they have a lower capacity to synthesize choline endogenously.

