1.5 Dose Rationale and Risk/Benefits

For children ages 1 to 3 years, the recommended dietary intake (RDI) for choline is 200 mg. and the maximum upper limit for tolerability is 1000 mg. (Food and Nutrition Board - Institute of Medicine, 1998). For children ages 4 to 8 years, the RDI for choline is 250 mg. and the maximum upper limit for tolerability is also 1000 mg. (eating two eggs would provide an equivalent of 545 mg. of choline). The goal of the current study is to provide choline supplementation as opposed to simply ensuring choline sufficiency. Our previous two studies used a fixed 500 mg. dose, regardless of the child's weight

CONFIDENTIAL

This material is the property of the University of Minnesota. Do not disclose or use except as authorized in writing by the study sponsor

(Wozniak et al. 2013, and Wozniak et al., 2015). The dose was well-tolerated, with partial or full doses received on 88% of the 270 days in the study. There was no difference between 500 mg. choline and placebo in terms of doses received or participant drop-out. There were no serious adverse events and no adverse events that differed by group other than fishy body odor in the choline group (an expected adverse event). A substantial proportion of children in the choline group (52%) compared to the control group (4%) did experience fishy body odor at some point in the 9 month study. For the smallest children in the study by weight, nearly 100% experienced fishy body odor at some point.

For the current study, choline will be given at a 19 mg per kg dose, based on evidence from the prior two pilot studies showing increased rates of fishy body odor at higher doses and also on data indicating that memory performance was optimal at doses in the 19 mg per kg range. Choline will be administered in the form of a fruit-flavored drink mix containing choline bitartrate (compounded for the study by Fagron, St. Paul, MN; Investigational New Drug Application #107085). Balchem (New Hampton, NY) manufactures the choline bitartrate to USP standards. The parent will add the powder to plain water. The matching placebo drink mix (without choline bitartrate) will also be provided by Fagron. Material will be stored, labeled, allocated, and dispensed by the University of Minnesota's Investigational Drug Service (IDS) Pharmacy.

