Participant families will be given a 65 day supply initially. Re-supply will be handled by packages mailed after the investigators have verified the participant's continued involvement in the study and freedom from serious adverse events during telephone visits. The preparation, coding, and tracking will be handled by the University of Minnesota's Investigational Drug Service pharmacy.

Choline is considered a GRAS substance (generally regarded as safe) by the FDA and the dose to be utilized in this study is lower than the maximum tolerable upper limit. Based on our previous study, tolerability for this lower dose of choline is expected to be high. Parents will be educated at the time of enrollment about potential side effects of choline which rarely occur and usually at much higher doses than those proposed (hypotension has been reported at 7.5 grams per day; gastrointestinal symptoms (loss of appetite, upset stomach), sweating, or body odor have occurred at 10-16 grams per day). As indicated, in the first 60 participants, we only observed fishy body odor and not other adverse events.

At one month, a full range of potential side effects will be screened. Although allergic reactions to choline are not expected (we observed none in the pilot studies), we will monitor for a range of allergic symptoms nonetheless. Adverse events and serious adverse events will be reported to the University of Minnesota IRB and to Quorum IRB. Serious adverse events will also be reported to the NIH program officer.

CONFIDENTIAL

This material is the property of the University of Minnesota. Do not disclose or use except as authorized in writing by the study sponsor

2. Study Objectives

Primary Objective

Evaluate the efficacy of choline in treating memory deficits and executive functioning deficits in children with FASD.

Secondary Objectives

Evaluate the long-term effects of choline supplementation by re-assessing children who took choline and placebo as part of the previous pilot study.

Evaluate the potential interaction between genotype ((for example PEMT, rs12325817) and response to choline intervention.

3. Study Design

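### A pooled age-by-treatment test would reuse the pilot data that suggested the age effect, and would mix two dose regimens in which pilot mg/kg varies with weight

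*Combined protocol and SAP*

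**What the plan says.** The closing sentence of Section 7.1 proposes, for a subset of outcomes, to combine the 60 pilot children with the 60 new ones, and says that this "will provide additional power to further evaluate age, sex, and PEMT genotype as moderating variables".

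Section 1.4 describes the larger pilot as having "a total of 40 additional participants, ages 2.5 to 5 years" and reports that, relative to placebo, "choline supplementation improved 2-3 year old children's performance on an elicited imitation paradigm". It gives no interaction test, p-value or effect size by age. The same section bases the PEMT hypothesis on the gene's role in endogenous choline synthesis and reports no PEMT-by-treatment result. No pilot result by sex appears anywhere.

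On dose, Section 1.5 states: "Our previous two studies used a fixed 500 mg. dose, regardless of the child's weight". The new trial gives 19 mg/kg, and the Study Summary adds a typical range of 200-425 mg and a 500 mg maximum. Section 1.5 also says that pilot memory performance was best at around 19 mg/kg.

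Section 2 lists as a secondary objective "Evaluate the potential interaction between genotype" and response to choline. Age and sex are in no objective. Section 7.2 names mixed-model growth curves under intention to treat but specifies no moderator model, study term, dose term or new-trial-only moderator analysis. Section 7.3, on analysis populations, is marked as not applicable.

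**The concern.** Two separate problems arise.

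The first is reuse of data and concerns age. A test that includes the children in whom the age pattern was noticed starts with that pattern already in its favour. It could reach significance when the new children show no age interaction. A reader would then take as independent support something that is largely the pilot result counted again.

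The second is the mixture of regimens. In the pilots mg/kg fell as weight rose, and weight rises with age. In the new trial mg/kg is constant up to the cap. The pilot age-by-treatment contrast therefore includes any dose-by-treatment effect and is not the same quantity as the new-trial contrast. Averaging the two gives an estimate without a clear meaning.

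What is at stake is the trial's conclusion about which children respond. The primary treatment comparison is not affected.

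**Working it through.** **The plan's own figure.** The only computed figure in 7.1 is 58.5 participants for the main comparison; no power is given for the moderator tests. A plain two-sided comparison at d = 0.66 needs 72.1 in total before rounding. A slope model with visits at 0, 6 and 9 months returns 58.5 if the within-child correlation is about 0.58. The variance inputs are not stated, so the figure can be neither confirmed nor faulted, and it does not bear on this point.

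**Reuse of the pilot data (age).** Let w be the share of children who come from the data that suggested the effect. With no true interaction,

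Z_pooled = √w × Z_pilot + √(1−w) × Z_new,

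where Z_new is standard normal. As a hand check, take w = 0.5 and a pilot interaction exactly at z = 1.96. The pooled test then rejects in the same direction if Z_new > 1.96√2 − 1.96 = 0.812, which has probability 0.208.

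The documents give no pilot z, so the table averages over pilot results that were significant by chance (4 million draws). In case A the pilot interaction itself was significant. In case B only the effect in the younger children was required to be significant, with two equal age groups and Z_pilot = (Z_young − Z_old)/√2. The second figure in case B also requires the older group to be non-significant.

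| Children from the generating data | Case A | Case B |
|---|---|---|
| 60 of 120 (both pilots suggested it) | 33.8% | 18.5% / 17.6% |
| 40 of 100 (larger pilot only, pooled alone) | 27.4% | 15.7% / 15.0% |
| 40 of 120 (larger pilot suggested it, all pooled) | 23.1% | 14.1% / 13.6% |

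In the case B simulations the test in the new children alone rejects in 4.9-5.0% of draws in every row.

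**Size of the dose difference.** At 19 mg/kg, the Summary's range implies weights of 200/19 = 10.5 kg to 425/19 = 22.4 kg. At those weights the pilot dose was 500/10.5 = 47.5 mg/kg down to 500/22.4 = 22.4 mg/kg, that is 2.5 down to 1.18 times the new regimen. The two coincide only at 500/19 = 26.3 kg.

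**Effect of the dose difference on the age test.** The documents give no age-weight relation and no dose slope, so these are assumptions: age uniform from 2.5 to just under 6 years; mean weight 13 kg at 2.5 years, rising 2.2 kg per year, SD 1.8 kg; residual SD 1; one outcome per child; 60 children per study; 3,000 runs per setting. The effect depends on mg/kg and not on age.

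| Change in effect per 10 mg/kg | Pooled | With study and study-by-treatment terms | New trial alone |
|---|---|---|---|
| 0 | 5.3% | 5.3% | 4.9% |
| 0.2 SD | 6.0% | 6.1% | 5.0% |
| 0.4 SD | 6.7% | 6.9% | 4.6% |
| 0.66 SD | 11.1% | 11.4% | 5.0% |
| −0.4 SD | 7.1% | 7.2% | 4.6% |

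The simulation error is about √(0.05 × 0.95/3000) = 0.4 percentage points, so the smallest of these departures is barely distinguishable from 5%. The study terms do not remove the confounding, because it lies within the pilots.

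**What the restriction costs.** For a 50:50 moderator, 1:1 allocation and a difference of 0.66 SD between subgroup effects, SE = √(4/(N/2) + 4/(N/2)). This is 0.516 at N = 60 and 0.365 at N = 120, giving power of about 25% and 44%. The difference detectable with 80% power is 2.80 × SE, or about 1.45 SD and 1.02 SD.

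**The case against.** The sentence in 7.1 is modest. It covers some outcomes only, speaks of evaluating further, makes no confirmatory claim, and does not exclude an analysis of the new trial alone. All of that stands. But no other moderator analysis is specified either, so the plan leaves the standing of the pooled age result open.

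A reader might infer that all three pooled tests are circular. The documents do not support that. No pilot result by sex or PEMT-by-treatment is reported, and the genotype hypothesis has a biological rationale. Section 1.4 speaks of evaluating the gene further, which hints at an earlier look but states no finding. Genotype also has no stated link to weight, so the age-dose confounding does not carry over to it. Nor does the secondary objective on genotype raise the stakes of the age problem.

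A reader might also take 34%, or more, as the size of the inflation. That needs a significant pilot interaction, whereas Section 1.4 reports a benefit in a subgroup. It also needs both pilots to have generated the finding, whereas the text places it with the 40-child trial.

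Finally, a reader might infer that the pilot dosing produced the younger-child benefit. Taken at face value, Section 1.5 points the other way. Under a fixed 500 mg, 19 mg/kg is reached only at about 26 kg, so an optimum there would favour heavier, generally older children and would tend to mask a benefit in the youngest.

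**Conclusion.** The point holds for age and is limited in size. Given the reported pilot finding and no true interaction, the pooled age test has an error rate of about 14-18% or about 23-34%, depending on whether the pilot evidence was a subgroup effect or an interaction. These are conditional rates that assume a chance finding in the pilots; they are not the level of a pooled test fixed before the pilots were seen. Dose-age confounding adds a smaller disturbance, about 6-11% against 5% under assumed weights and slopes, in a direction the documents do not settle. For sex and genotype only the heterogeneity from mixing two regimens remains.

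Nothing here supports dropping the pooled analysis, or moving all three moderators to a test in 60 children. At 25% against 44%, neither analysis is well powered, and giving up the extra precision for sex and PEMT would be a debatable exchange.

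**What to change.** In Sections 7.1 and 7.2:

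1. For age, estimate the treatment-by-age (by time) term in the new 60 children alone. Report it with its confidence interval beside the pilot and pooled estimates, and base any claim of replication on the new-trial estimate.
2. In every pooled moderator model, include study and study-by-treatment terms. As a sensitivity analysis, let the moderator effect differ by study and enter the actual mg/kg for pilot children. This is not suitable as the main pooled model: a moderator effect that differs freely by study is estimated separately in each, which gives up the precision for which pooling was proposed.
3. Keep the pooled sex and PEMT analyses for precision and label them exploratory.

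The cost is a few sentences and one or two extra models, with no change to recruitment, procedures or dosing. The downside is the low power of the new-trial age test, so a non-significant result there should be read from its interval and not as evidence of no moderation.
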